|--------------------------------|--|
| TITLE | The MAGNIFI Trial: Metastasis assessment with Gallium-68 PSMA and Nanoparticle Imaging Fusion International |
| SHORT TITLE | Magnifi Trial |
| VERSION NO. | 2.4 24 th January 2019 |
| SPONSOR | The Garvan Institute of Medical Research [name] |
| INDICATION | Diagnosis and treatment of lymph node metastases in men with prostate cancer |
| OBJECTIVES | 
1. To compare “Combidex” Nanoparticle-Magnetic Resonance Lymphography (Nano MRL) and 68Ga-PSMA positron emission tomography (PET) to the gold standard and current practice; the histology of pelvic lymph node dissection, to locate the position of lymph nodes
 
2. Determine whether concordance of these two imaging technologies (68Ga-PSMA PET - functional imaging, and Nano MR - anatomical imaging) is worse, better or equal to lymph-node dissection
 |
| TRIAL DESIGN | An investigator initiated, prospective, non-randomized study |
| PLANNED NUMBER OF PARTICIPANTS | 120 participants will be recruited over a two year period; 60 participants from St Vincent’s Hospital Sydney and 60 participants from the Wesley Hospital Brisbane |
| TARGET POPULATION | Men diagnosed with prostate cancer with and without suspicion of lymph node involvement but have yet to undergo a radical prostatectomy. |
| INCLUSION CRITERIA | 
 • Male, aged 18 years or over • Confirmed adenocarcinoma of prostate and at least clinical stage T3A and/or Gleason sum $\geq 4+3=7$, or preoperative PSA ≥ 15 ng/ml and planned radical prostatectomy • Suspected lymph node involvement pre- radical prostatectomy based on Briganti nomogram $\geq 10\%$. • Suitable for radical prostatectomy and pelvic lymph node dissection, as per institutional guidelines and not yet treated pre-prostatectomy • Subject is able to understand and willing to sign the participant information statement and consent form • Subject is expected to remain available for 24 months of clinic visits |
| EXCLUSION CRITERIA | 
 • Past history any other type of cancer (except skin cancer). • Previous treatment for prostate cancer (surgery, radiotherapy, chemotherapy, hormone androgen deprivation therapy) • Proven bony metastatic disease, visceral metastases or lymph node metastases above the level of the aortic bifurcation |

| | |
|--|---|
| | 
 • Previous surgery in pelvis (e.g. bilateral hip replacement) that limit the extent of pelvic lymph node dissection • Patients who refuse radical prostatectomy or pelvic lymph node dissection • Patients who refuse to join the trial or are unable to consent • Patients not being considered for further therapy • Patient has absolute contra-indications to undergoing MRI scanning • Patients who cannot lie still for at least 60 to 75 minutes or comply with imaging • Subject has medical conditions that would limit study participation (per physician discretion) • Subject is enrolled in one or more concurrent studies that would confound the study results of this study as determined by the study investigators • Subject has a limited life expectancy that would not allow completion of the 24 month visits |
| STUDY PROCEDURES St Vincent's Hospital, Sydney | 
 1. Men diagnosed with prostate cancer are referred to a participating urologist for a radical prostatectomy 2. The patients are consented to the study by the urologist following fulfilment of the selection criteria 3. The patient is referred to the Department of Nuclear Medicine, St Vincent's Hospital, Sydney 4. The 68Ga-PSMA PET Scan is performed at the Department of Nuclear Medicine, St Vincent's Hospital, Sydney 5. On the return visit, "Combidex" is administered to the patient and the patient is referred to Medscan Barangaroo for a MRI scan 6. Radiologist and Urologist annotate suspect lymph nodes using the Pelvic Lymph Node Diagnostic Template and assign index of suspicion to each area 7. Patient undergoes radical prostatectomy including the removal of lymph nodes 7-10 days following Combidex nano-MRL 8. The prostate and the lymph nodes are sent to histology for reporting 9. Analysis: 
 a. Histology Vs Nano-MRL b. Histology Vs Ga68 PSMA PET c. Histology Vs Nano-MRL Vs Ga68 PSMA PET 10. Repeat Ga68 PSMA and Nano-MRL if not concordant with Histology within 6-8 weeks of surgery 11. Follow up Visits: The participant will have clinical follow up reviews as part of their care at 6 weeks, 2 months, 6 months, 12 months and 24 months 12. Participant will complete the Expanded Prostate Cancer Index Composite (EPIC) survey at baseline (prior to surgery), 6 weeks, 3 months, 6 months, 1 years and then yearly for a minimum of 5 years). |
| ENDPOINTS | 
 1. Diagnostic: 
 a. Concordance of 68Ga-PSMA PET and Nano MRL |

| | |
|----------------------|---|
| | 
 b. Histology of LND c. Concordance of (a) and (b) d. Results of reimaging after LND 
2. Clinical – Follow up at 24 months
 |
| STATISTICAL ANALYSES | We will recruit 120 patients. Considering that each patient has 6 packets (a lump of fat containing lymph nodes) on average, we will be comparing 720 packets in total. This number will give 90% power to detect a 10% or less discordance between final histology analysis and the combined imaging modalities consensus. |
| STUDY DURATION | 10 years (Anticipated January 2016 to December 2026) |

CONTENTS

| | |
|--|-----------|
| 1. BACKGROUND | 9 |
| 1.1. DISEASE BACKGROUND | 9 |
| 1.2. RATIONALE FOR PERFORMING THE STUDY | 11 |
| 2. STUDY OBJECTIVES | 12 |
| 2.1. PRIMARY OBJECTIVE | 12 |
| 2.2. SECONDARY OBJECTIVES | 12 |
| 3. STUDY DESIGN | 12 |
| 3.1. DESIGN | 12 |
| 3.2. STUDY GROUPS | 12 |
| 3.3. NUMBER OF PARTICIPANTS | 12 |
| 3.4. NUMBER OF CENTRES | 13 |
| 3.5. DURATION | 13 |
| 4. PARTICIPANT SECTION | 13 |
| 4.1. INCLUSION CRITERIA | 13 |
| 4.2. EXCLUSION CRITERIA | 13 |
| 5. STUDY OUTLINE | 14 |
| 5.1. STUDY FLOW CHART | 14 |
| 5.2. INVESTIGATION PLAN | 15 |
| 5.3. STUDY PROCEDURE RISKS | 17 |
| 5.4. RECRUITMENT AND SCREENING | 18 |
| 5.5. INFORMED CONSENT PROCESS | 18 |
| 5.6. ENROLMENT PROCEDURE | 18 |
| 6. SAFETY | 18 |
| 6.1. ADVERSE EVENT REPORTING | 18 |
| 6.2. SERIOUS ADVERSE EVENT REPORTING | 18 |
| 6.3. DATA SAFETY AND MONITORING BOARD | 19 |
| 6.4. EARLY TERMINATION | 19 |
| 7. STATISTICAL CONSIDERATIONS | 19 |
| 8. CONFIDENTIALITY AND STORAGE AND ARCHIVING OF STUDY DOCUMENTS | 21 |
| 9. FUNDING | 22 |
| 10. OTHER STUDY DOCUMENTS | 22 |
| 11. REFERENCES | 33 |

1.BACKGROUND

1.1. DISEASE BACKGROUND

Following curative intended therapy in prostate cancer patients, a high proportion of patients (approx. 25%) relapse with local and/or distant recurrence [1]. The metastasis of a lymph node (LN) in a patient with prostate cancer means that the disease has become systemic with the increased risk of disease progression. Therefore the ability to detect the presence of LN metastasis is important in terms of disease prognosis and treatment selection. In the past, patients with LN metastasis have had poor prognoses due to the scarcity of accurate staging techniques and toxic treatment regimens such as radiotherapy. For those patients with a medium to high risk of having LN metastasis, the current procedure is a bilateral pelvic lymph node dissection (LND). It is generally accepted that a LND provides important information for prognosis which cannot be matched by other current procedures. Therefore, it is the standard procedure prior to curative treatment with either radical prostatectomy or radiation therapy. Besides being a staging procedure, pelvic LND may be curative, or at least beneficial, in a subset of patients with limited lymph node metastases [2, 3]. The number of nodes removed during LND has been significantly correlated with the time to progression [3, 4]. However, results from ongoing prospective studies are awaited. On the other hand, the LND is not optimal due to the frequent inability to remove all suspicious lymph nodes within the dissection area. 41% of metastatic LN disease is not found [5], due to these LN being outside the routine surgery field. As a result, many urologists will perform an extended lymphadenectomy (e-LND), which leads to extended operating times and the risk of complications [6]. Also, radiotherapy of LN metastases has limitations: more than 50% of metastatic LN are outside the routine (RTOG-CTV) radiation field [7]. As a result, the effect of standard salvage LN radiotherapy is limited [8]. Currently used imaging techniques such as CT and conventional MRI are not sensitive enough to detect prostate cancer metastases due to the small size of the nodes (< 8mm) [9]. Finally, 11C-Choline PET/CT fails to detect metastatic LN, when they are smaller than 6 mm since a minimum amount of tracer needs to be present in the LN to be detected [10].

It has been suggested that patients with metastatic LN ≤ 8 mm have a significantly better 5-year distant metastases-free (79% vs 16%) and overall survival (81% vs 36%), than patients with larger positive lymph nodes [11]. Thus detection and localization of most –small- LN and subsequent focused, patient tailored treatment of these small metastatic LN may reduce side effects and enable cure [12, 13].

An accurate non-invasive imaging modality in combination with existing treatment techniques, may lead to a therapeutic shift for patients who have in the past been restricted to palliative treatment. Recently developed imaging modalities to detect small lymph node metastases, which offer promise, include Nano Magnetic Resonance (Combidex) Lymphography (Nano MRL) and 68Gallium-Prostate Specific Membrane Antigen (PSMA) Positron Emission Tomography Imaging (68Ga-PSMA PET). However, the true value of 68Ga-PSMA PET and Nano MRL is still unknown, underscoring the need for well designed further studies with histopathology as the standard as reference.

Recently developed imaging modalities to detect small lymph node metastases

Nano MRL (Combidex)

Nano MRL is a non-invasive technique, which can be used to detect small prostate cancer lymph node metastases [14-17]. Currently, lymph node staging is performed with the use of invasive pelvic lymph node dissection (LND). Literature shows three potential advantages of the use of Nano MRL for lymph node staging in men with newly diagnosed prostate cancer: 1) a negative Nano MRL will preclude a LND; 2) a positive Nano MRL supports LND lymph node staging, and can “target” the dissection; and 3) a positive Nano MRL might improve the opportunity for curative treatment in patients with limited lymph node involvement [17].

Intravenous Nano-MR, using dextran coated small iron oxide particles (ferumoxtran-10, Combidex®, Radboudumc, The Netherlands), allows detection of metastatic LN in even very small (>2 mm) LN [14-16]. Thus Nano-MR results in a significant improvement of the detection of LN metastases compared to other existing techniques [14-16]. For example, compared to 11C-Choline PET/CT, Nano-MR detected more metastatic LN (738 vs 132) in more patients (23/29 vs 13/29) in smaller LN (mean diameter 4.9 vs 8.4 mm)[18]. Nano-MR also obviates the use of surgical removal of LN [5, 16], and thereby reduces unnecessary side effects and decreases health care costs. A large prospective multi-centre study demonstrated the cost-effectiveness [10, 19]. Furthermore, with Nano-MR LN metastases are more accurately detected than with current nomograms [20, 21]. Nano-MR images can guide selective radiation of small, thus far undetected metastatic LN [12], and is expected to improve patient outcomes again [13, 22]. No prospective data is available comparing Nano-MR with 68Ga-PSMA.

History:

Approximately 15 years ago Nano MRI using Combidex became available for human use. The data from primary pharmacokinetic studies, a Phase I study and the data in a Phase II study were consistent, despite the different designs and rates of administration of the contrast agent. These studies showed:

1. A single intravenous dose of Combidex up to 1.7 mg Fe/kg is safe and tolerated. MRI results demonstrated the agent's ability to affect imaging characteristics of the blood pool, well-perfused organs, and cervical LN.
2. The Combidex doses of 1.1, 1.7, 2.6 and 3.4 mg Fe/kg could be safely administered. Signal intensity data and specificity rates for detecting normal LN demonstrated that the best imaging results were achieved with doses of 2.6 and 3.4 mg Fe/kg when MRIs were obtained 24 or 36 hours after Combidex administration. Because the results for those two doses and two imaging times were similar, the lower dose (2.6 mg Fe/kg) was chosen as the dose to be used in Phase III LN studies, with an imaging time of 24 to 36 hours. Pharmacokinetic results were similar to those from other studies, suggesting that the elimination of Combidex is unaffected by the rate of administration.
3. The administration of Combidex at the doses proposed (1.1 and 2.6 mg Fe/kg) has no immediate or delayed effect on immune function. The pattern of immune cell activity in the Combidex groups was similar to that in the placebo group during 8 weeks of pre-dose evaluations and 6 months of post-dose evaluations.
4. The pharmacokinetics of Combidex were linear in the range of doses tested. The half-life is 25 to 30 hours. There were no differences between the sexes in any pharmacokinetic parameters. Signal intensity analyses showed that the maximum contrast effect of Combidex occurred immediately after dose administration for liver and spleen and 24 hours after administration for lymph nodes. Most of the changes in signal intensity disappeared from LN within 7 days after administration of the dose recommended for lymph node MRI (2.6 mg Fe/kg). Assays of serum ferritin showed that total body iron stores were elevated to maximum levels 72 hours after dose administration and then slowly returned to normal.

In the US, two attempts were made to register Combidex through the FDA for clinical lymph node imaging, two similar attempts were made by Guerbet in Europe (under sublicensing) by EMEA. All four attempts failed due to suboptimal trial design, suboptimal statistics, and suboptimal central reading of imaging studies.

Finally in December 2007 the last application was withdrawn. The CHMP (EMA) stated that, despite potential benefits and an acceptable safety profile; the pivotal study failed to demonstrate a consistent and statistically significant benefit for Combidex in sensitivity and failed to confirm non-inferiority with regards to specificity. All outstanding issues on quality, non-clinical documentation,

and clinical safety were, however, resolved before dossier withdrawal. A summary of the evaluation of the EMEA CHMP registration process, concerning the value and safety of Sinerem/Combixel is attached.

The Oncology Drugs Advisory Committee published a briefing document on Combixel in 2005 is attached. They concluded that Combixel could be safely administered by slow infusion over a period of approximately 30 minutes following dilution in 100 ml of normal saline. This method of administration minimizes adverse events and allows management of adverse events that may occur by stopping the infusion. The rate of serious events is less than a third of the rates experienced with iodinated contrast agents currently used with CT.

68Ga-PSMA PET Imaging:

Prostate specific membrane antigen (PSMA) is a cell-surface protein, which is significantly overexpressed in prostate cancer cells when compared to other PSMA-expressing tissues [23, 24]. Additionally, an up-regulation of PSMA was shown in tumour cells of patients with hormone-refractory prostate cancer [25, 26] as well as a significant increase in PSA recurrence [27]. Overall, PSMA provides a promising target for prostate cancer-specific imaging. Recently methods have been developed to label PSMA ligands with 68Ga to enable their use for PET imaging [28, 29]. A study by Afshar-Oromieh et al evaluating PET/CT using a 68Ga-labelled PSMA ligand suggests that this novel tracer can detect prostate cancer relapses and metastases with high contrast by binding to the extracellular domain of PSMA, followed by internalization [30, 31].

In recent studies the use of 68Ga-PSMA is compared with the current standard of choline PET-CT using 18-fluoromethylcholine in the diagnosis of disease recurrence[32, 33]. Overall, 68Ga-PSMA was more sensitive than PET-CT using 18-fluoromethylcholine for the detection of prostate cancer recurrence in patients with low PSA values. In the study by Morigi et al, in men with PSA <0.5ng/ml the detection rate of 68Ga-PSMA and 18-fluoromethylcholine was 50% and 12.5% respectively, for PSA 0.5-2.0 ng/ml 69% and 31% respectively (p-values all <0.05). A drawback to this studies is that only a small number of patients had histological correlation performed with imaging findings, however in this small group there were no false negative or false positive findings.

1.2. RATIONALE FOR PERFORMING THE STUDY

The current lack of imaging techniques to detect lymph node metastases and the realization of the variability of the lymphatic drainage of the prostate has led to: 1) inadequate treatment of positive nodes outside the usual fields, 2) many thousands of negative node dissections and 3) the recurrence of PSA after treatment due to unrecognized or untreated nodal metastases. Promising emerging imaging technologies including 68Ga-PSMA PET and Nano-MR Lymphography are now available but are yet to be validated in the clinical environment. An accurate non-invasive imaging modality in combination with improved treatment techniques, may improve the treatment outcomes in terms of survival (more specific and extended LND) and morbidity (exclude a high percentage of patients from an unnecessary LND) in prostate cancer patients with high risk of lymph node metastases.

2. STUDY OBJECTIVES

Hypothesis:

THE ADVANTAGES OF ACCURATE NODAL IMAGING FOR PATIENTS WITH INTERMEDIATE AND HIGH-RISK PROSTATE CANCER:

- (i) If combined anatomical and functional nodal assessment is negative, then patients do not need a node dissection.
- (ii) If combined anatomical and functional nodal assessment is positive, then appropriate treatment to the nodes (in conjunction with treatment to the primary cancer) can be planned. This may involve:
 - (a) Anatomically targeted node dissection (in place of e-LND)
 - (b) Anatomically targeted radiotherapy dose-painting
 - (c) The use of systemic chemotherapy (multiple small nodes in many locations) followed by the use of hormonal treatment (protocols analogous to those used in breast cancer oncology).
- (iii) This multi-modal approach will decrease the failure rate of current treatment protocols where nodal status is unknown and standard nodal fields are irradiated or dissected based on probability.

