After dissection, the specimens will be sent to pathology for histopathological examination. The lymph nodes will be reviewed at 2mm dissections. The result of histological examination of the lymph nodes (gold standard) will be compared with the result of 68Ga-PSMA PET scan and Nano MRL. Sensitivity, specificity, positive predictive value (PPV), and negative predictive value (NPV) for Nano MRL and Ga68-PSMA PET scan in pelvic lymph nodes with corresponding CT size measurement in comparison with histopathology will be assessed for detection of lymph node metastases.

Analysis will include assessing sensitivity, specificity, diagnostic accuracy, positive and negative predictive values for different levels of Nano MRL and PSMA PET avidity in pelvic lymph nodes with corresponding CT size measurement in comparison with histopathology.

5. *Re-imaging*

In participants where the 68Ga-PSMA PET and/or Nano MRL detected metastases in the lymph nodes but these were not seen in the histopathology (i.e., a false positive result), the participant will undergo a repeat PSA test, a 68Ga PSMA PET scan and a Nano MRL 6 weeks after the radical prostatectomy to confirm the accuracy of the original results and to ensure that no other sites of metastases missed. As noted in section 5.3, correspondence from [name] (Appendix D) and from clinical evidence to date, there have been no safety issues as a consequence of having a repeat 68Ga PSMA PET scan and/or a Nano MRL. All precautionary safety measures will be performed.

6. Follow up visits

As part of the participant's clinical care, follow up consultations with the treating urologist are planned for 6 weeks, 2 months, 6 months, 12 months and 24 months post surgery.

7. Quality of Life (QOL) survey

To determine the outcome of treatment, the participant will be asked to complete the self-reporting Expanded Prostate Cancer Index Composite (EPIC) survey. The EPIC survey has been extensively used to report on the physical, emotional and psychological outcomes of the prostate cancer patients. The participant will ask to complete the survey at baseline (prior to surgery), at 6 weeks, 3 months, 6 months, 1 year and then yearly for a minimum of 5 years.

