7. STATISTICAL CONSIDERATIONS

a) Trial Size:

We will now recruit 120 patients (60 from St Vincent’s Hospital, Sydney and 60 from the Wesley Hospital, Brisbane) from the originally planned 80 patients. Based on the previous calculation, that each of the 80 patients will have 6 packets (a lump of fat containing lymph nodes) on average, we will be comparing 480 packets in total. This number will give 90% power to detect a 10% or less discordance between final histology analysis and the combined imaging modalities consensus. Sample size was calculated based on agreement of combination of both images together with histology. We used 15% as the probability of positive lymph node from histology results, based on literature the probability of positive lymph node result from histology is between 11% and 17% [35].

For 95% sensitivity and 90% specificity of combination of the two images, we need to test 178 packets. To achieve this number of packets we need to recruit a maximum of 32 patients. To account for correlation between packets from each patient, we have considered high effect size of equal to 2.5 which results in the requirement of 80 patients. The new recruitment target will exceed this requirement.

Statistical calculations for the MAGNIFI trial sample size are set out below:

The data for N patients, with n packets per patient, will be tabulated as follows:

| Combined Test | Histology | | Total |
|---------------|-----------|----------|-------|
| | Positive | Negative | |
| Positive | A | B | A+B |

| | | | |
|----------|-----|-----|-----|
| Negative | C | D | C+D |
| Total | A+C | B+D | N×n |

To take account of clustering, a variance inflation factor VIF is calculated as follows:

$$VIF = 1 + (n-1)\rho$$

where n is the number of packets per patient (6) and ρ is the intra-class correlation, a measure of clustering within patients (assumed to be a maximum of 0.3). This yields a VIF of 2.5.

The formula for the sample size for a two sided McNemar test, taking into account the VIF, is then (based on reversing equation (5) of Gönen, 2004):

$$N = \frac{(z_{1-\alpha/2}\phi + z_{1-\beta}\sqrt{\phi^2 - 0.25\delta^2(\phi + 3)})^2}{n\phi\delta^2/(1 + (n\phi - 1)\rho)}$$

where:

z is a percentile from the standard normal distribution

α is the level of significance (two-sided test, α = 0.05)

1-β is the power (assumed to be 0.90)

φ is the total proportion of discordant pairs: (B+C)/ (N×n) in above table

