δ is the difference in the proportions of the two types of discordant pairs: (B-C)/ (N×n)

n = number of observations per patient (6)

For the calculations, it was additionally assumed that the proportion of positive packets was 0.15, φ = 0.10, and δ = 0.04. This assumes the following proportions:

[figure not shown]
| Combined Test | Histology | | Total |
|---------------|-----------|----------|-----------|
| | Positive | Negative | |
| Positive | 0.12 | 0.07 | 0.19 |
| Negative | 0.03 | 0.78 | 0.81 |
| Total | 0.15 | 0.85 | N×n = 480 |

Gonen M. Sample size and power for McNemar's test with clustered data. *Statistics in Medicine* 2004, 23: 2283-2294

b) Statistical Analysis:

We will compare 'packet concordance rate' between histology and MR Lymphography using a MRA arterial map (that can be acquired at the MRL) to locate the position of the lymph node, the 68Ga PSMA PET SCAN plus a combined evaluation, and histology. As indicated in the diagram below, lymph nodes are removed by one lump of fat (region-packet) at a time (refer to region-packets 'a' to 'f' in figure below). The two tests (MR lymphography and 68Ga PSMA PET) will indicate (with error)

whether each node is positive or not, and thus whether each region-packet is positive (at least one node positive) or not (no nodes positive). The combined evaluation is a consensus of the two tests: region-packets are positive if one or both tests indicate positive and negative only if both tests indicate the region-packet is negative. Using histology, we can assess the accuracy of the two tests (plus combined evaluation) in terms of false positives.

| | Histology | MR Lymphography | Ga68 PSMA | Imaging Consensus |
|---|-----------|-----------------|-----------|-------------------|
| a | Negative | Negative | Negative | Negative |
| b | Positive | Positive | Positive | Positive |
| c | Negative | Positive | Positive | Positive |
| d | Negative | Negative | Negative | Negative |
| e | Positive | Positive | Positive | Positive |
| f | Positive | Negative | Negative | Negative |

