We will calculate the CONCORDANCE rate for positive nodes in each packet with their corresponding region on imaging, both against each individual imaging modality and against a summed score from both imaging techniques. Sensitivity, specificity, negative predictive values (NPVs), and positive predictive values (PPVs) will be reported [31, 32]. The maximum likelihood estimates (MLEs) of PPV and NPV will be calculated from the MLEs of the sensitivity, specificity, and prevalence rate. Hierarchical modelling will be used to test for concordance between matched results from each packet.

Secondary outcome of interest is quality of life and the complications. As part of initial longitudinal analyses quality of life (as measured using EORTC-QLQ-C30) will be evaluated using one-way ANOVA. To examine differences in quality of life scores between the two groups (standard eLND versus super-eLND), baseline characteristics will be compared between groups to assess whether the groups are balanced using Chi-square tests and Fisher's exact tests. The additional analysis involves comparing the change in quality of life scores (worsened, stable or improved quality of life) from baseline to 2 and 6 months between the groups using Chi-square tests and Fisher's exact tests. Similar method will be used evaluating the differences in the complication score.

c) Interim Analysis:

An analysis of the data will be performed after every 10 patients have completed imaging and pelvic lymph node dissection. This will allow the trial statistician and data monitoring committee to identify any problems or discrepancies with data collection and recording, in addition to identifying any possible technical issues that might jeopardise

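### Hypothesis (i) concerns omitting dissection in a whole patient, but every planned accuracy measure is per packet or per node, so no planned measure tests it

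*Protocol*

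**What the plan says.** Section 2 lists, under the label Hypothesis, the statement "If combined anatomical and functional nodal assessment is negative, then patients do not need a node dissection". The rationale in section 1.2 gives the same purpose, to "exclude a high percentage of patients from an unnecessary LND". Both are statements about a man, not about a region of his pelvis.

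Section 7 works with a different unit:

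- The sample-size table totals N×n packets, "where n is the number of packets per patient (6) and ρ is the intra-class correlation".
- The combined reading is defined region by region: "region-packets are positive if one or both tests indicate positive and negative only if both tests indicate the region-packet is negative".
- The main comparison is worded "We will compare 'packet concordance rate' between histology and MR Lymphography", and is extended to PSMA PET and to the combined evaluation.
- The model is per packet: "Hierarchical modelling will be used to test for concordance between matched results from each packet".
- The predictive values follow from the same set-up: "The maximum likelihood estimates (MLEs) of PPV and NPV will be calculated from the MLEs of the sensitivity, specificity, and prevalence rate".

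Section 5.2, item 4 (Histopathology) lists sensitivity, specificity and predictive values "for Nano MRL and Ga68-PSMA PET scan in pelvic lymph nodes with corresponding CT size measurement in comparison with histopathology", which reads as node level.

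No section says when a man counts as negative on imaging or on histology, and none names a per-patient sensitivity or NPV. Section 7b speaks of judging accuracy through false positives, whereas hypothesis (i) turns on false negatives.

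**The concern.** Hypothesis (i) needs one quantity: among men whose imaging is negative everywhere, the proportion with no nodal disease on histology. A man's disease is missed if any one of his regions is wrongly called negative. With about six packets per man he has about six chances of being missed, and a packet NPV counts each of them separately.

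The planned analysis can therefore be carried out in full and leave the hypothesis unanswered. The NPV that is available would be calculated on packets, most of which are expected to be histology-negative (85% in the design table). A reader who sets it beside the hypothesis would take the risk of missed disease in an imaging-negative man to be lower than it is. Precision would also look better than it is, because hundreds of packets stand in for a few dozen imaging-negative men.

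**Working it through.** **Inputs, all from protocol section 7a.** Six packets per man; 15% of packets positive; ICC at most 0.3, the value behind the variance inflation factor 1 + 5 × 0.3 = 2.5; 120 men. Two sets of accuracy figures are given: the design table (cells 0.12, 0.07, 0.03, 0.78), and a stated 95% sensitivity with 90% specificity.

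**Check of the table.** Total discordance is 0.07 + 0.03 = 0.10 and the difference is 0.07 − 0.03 = 0.04, as the protocol states. The table implies sensitivity 0.12/0.15 = 80% and specificity 0.78/0.85 = 91.8%.

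**Packet NPV.**

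- Design table: 0.78/0.81 = 96.3%, so 3.7% of imaging-negative packets hold disease.
- 95%/90%: (0.90 × 0.85)/(0.90 × 0.85 + 0.05 × 0.15) = 0.765/0.7725 = 99.0%, so 1.0% hold disease.

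**Patient NPV.** Let K be the number of histology-positive packets among a man's six. With reads independent given histology:

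NPV(patient) = P(K=0) × sp⁶ / Σₖ P(K=k) × (1−se)ᵏ × sp⁶⁻ᵏ

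The protocol gives no distribution for K. I assume a beta-binomial with mean 0.15 and ICC ρ, so a = 0.15(1/ρ − 1) and b = 0.85(1/ρ − 1). At ρ = 0.3, a = 0.35, b = 1.983 and P(K=0) = 0.588.

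- Design table, ρ = 0.3: the numerator is 0.588 × 0.918⁶ = 0.351 and the denominator 0.377, giving 93.0%.
- Design table, ρ = 0: this reduces to 0.963⁶ = 79.7%.
- 95%/90%, ρ = 0.3: 0.312/0.318 = 98.3%.
- 95%/90%, ρ = 0: 0.9903⁶ = 94.3%.

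| Accuracy assumed | Packet NPV | Patient NPV, ICC 0.3 | ICC 0.2 | ICC 0.1 | ICC 0 |
|---|---|---|---|---|---|
| Design table | 96.3% | 93.0% | 90.4% | 86.5% | 79.7% |
| 95% / 90% | 99.0% | 98.3% | 97.6% | 96.5% | 94.3% |

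**Clustered reading errors.** If reading errors also cluster within a man at ICC 0.3, the design-table figure at ρ = 0.3 falls from 93.0% to 92.0%, or to 91.3% if only the missed-disease errors cluster.

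**Where the two NPVs meet.** With independent reads, packet and patient NPV become equal at an ICC of about 0.50 (design table) or 0.47 (95%/90%). Both lie above the protocol's stated maximum.

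**Precision.** At ρ = 0.3 with independent reads, the expected number of wholly imaging-negative men is 120 × 0.377 ≈ 45 (design table) or 120 × 0.318 ≈ 38 (95%/90%). On the design table about 3 of the 45 would be node-positive. An observed 42/45 has an exact 95% confidence interval of about 82% to 99%.

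**The case against.** The strongest reply is that hypothesis (i) is motivation. Section 2 introduces the list as advantages of accurate imaging, and other items on it, such as planning systemic therapy and lowering treatment failure, are not tested by the accuracy analysis either. The primary objective in section 2.1 is to locate nodes, and for that the packet is the right unit. This narrows the point without removing it: the protocol labels the list as its hypothesis, and the rationale repeats the patient-level aim.

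A second reply is that a statistical analysis plan, not shown here, may add a per-patient summary. It may. But the protocol itself fixes the hypothesis, the unit, the table and the derivation of NPV, and these do not fit together.

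Three stronger readings are tempting and not supported:

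- A reader might infer that the trial will report an NPV that overstates the safety of omitting dissection. The protocol states no rule or threshold tying packet NPV to hypothesis (i). The overstatement arises only if someone reads the one against the other.
- A reader might say that every measure is per packet. Section 5.2 reads as per node. The accurate statement is that none is per patient.
- A reader might take a missed-disease rate of about 20% as the headline. That needs independent packets and the design table's 80% sensitivity. The protocol sizes on ICC 0.3 and also states 95% sensitivity, and at that ICC the gap then shrinks to 0.7 points.

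**Conclusion.** The concern holds as a mismatch between hypothesis and analysis unit: the plan contains no measure that tests hypothesis (i). At ICC 0.3 with independent reads, packet NPV exceeds patient NPV by about 3 points on the design table and by less than 1 point on the 95%/90% figures. About 2-7% of wholly imaging-negative men would have missed disease, up to about 9% if reading errors cluster, against 1-3.7% of imaging-negative packets. Under full independence the range for men is about 6-20%.

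The direction holds over the protocol's whole assumed ICC range, up to 0.3. The size rests on six packets per man, 15% positive packets, the beta-binomial form and whichever of the two stated accuracy assumptions is used. The packet analysis remains sound for localisation.

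**What to change.** In section 7b, add a per-patient analysis:

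- A man is imaging-positive if any assessed region is positive on the test concerned; for the consensus, on either test.
- He is histology-positive if any resected node is positive. This must include the targeted presacral and mesorectal nodes and any out-of-template nodes that section 5.2 allows to be resected. Restricting the table to the six template packets would count a man with disease only outside them as negative on both sides.
- Report per-patient sensitivity, specificity, NPV and PPV with exact confidence intervals, for each modality and for the consensus.
- Add a sensitivity analysis restricted to men whose packets were all recorded as complete, using the completeness label already collected under section 5.2.

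In section 2, state that hypothesis (i) is addressed by per-patient NPV and that packet results serve the localisation objective.

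The cost is wording and analysis time, with no new patients, procedures or data. The NPV will be less favourable and much less precise, since it rests on about 38-45 men at ICC 0.3 with independent reads, and the trial was not sized for it. The protocol should say so and present the per-patient NPV as an estimate with its interval.
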